### 9.2 SAMPLE SIZE DETERMINATION

Part 1: a sample size of greater than 50 participants will be powered (greater than 80%) to target a 95% confidence interval within 60% and 140% of the geometric mean estimates of 25(OH)D systemic clearance. The sample size assumes a coefficient of variation of 50% in 25(OH)D steady-state concentration.(48, 89) Based on prior experience (90, 91, 92, 93) a sample size of 16 participants in the interim analysis will suffice to determine a recommended dose for Part 2.

Part 2: For the optimal dosing regimen defined by the interim PK-analysis, the null hypothesis that the proportion of children who achieve a vitamin D level of greater than or equal to 40 ng/ml is 50% or less at 16 weeks will be tested against the alternative hypothesis that the proportion is 75% or more at the one-sided 0.05 significance level with power of 0.90. Using the one group Chi-square test for testing a single proportion, the number of study participants required to complete Part 2 is 31 participants. To allow for an approximately 30% dropout rate (due, in part, to the COVID-19 pandemic), 63 participants will be randomized to (A) the 8,000 IU daily dose (with a 50,000 IU loading dose) regimen or to (B) the standard of care (600 IU/day) dose. The allocation ratio will be 2:1 (A:B).

### 9.3 POPULATIONS FOR ANALYSES

**PK analysis Population:** All participants with at least 1 PK sample will be included in the population PK analysis.

**Intent-to-Treat (ITT) Population:** This population includes all enrolled participants. Analysis of the ITT population will be used for all non-PK analyses.

**Safety Population:** This analysis population includes all enrolled participants who received at least one dose of study treatment.

## 9.4 STATISTICAL ANALYSES

### 9.4.1 GENERAL APPROACH

Following finalization of the Protocol, but prior to 25% enrollment, a Statistical Analysis Plan (SAP) will be issued as a separate document, which will provide detailed analytical plans for the set of analyses outlined below. All statistical analyses will be conducted following the statistical principles for clinical trials as specified in International Conference on Harmonization Statistical Principles for Clinical Trials (ICH Topic E9). Any deviations from the planned analyses will be described and justified in the final integrated clinical study report. All study data and summary tables will be presented overall and by study sites.

Descriptive statistics for continuous data will be summarized using mean and standard deviation or median and interquartile range, as appropriate. Categorical data will be summarized using frequency and percent. Any outliers detected during data review will be investigated and methods for handling outliers or data transformation will be defined in the SAP.

### 9.4.2 ANALYSIS OF THE STUDY ENDPOINT

The study does not include an efficacy endpoint. The primary objective is to conduct a population PK analysis.

A population PK analysis will be performed to characterize the PK of vitamin D in overweight/obese children using the software Nonlinear Mixed Effects Modeling (NONMEM, version 7.2). Different structural PK models (e.g., 1 and 2 compartment) with linear or non-linear (e.g., Michaelis-Menten) kinetics will be fitted to the concentration-time data of 25(OH)D. Between-participant variability on model parameters and different residual error models will be tested. Model development will be guided by goodness of fit plots, plausibility of parameter estimates, and reduction in inter-individual variability for structural and residual error parameters, as well as objective function and shrinkage values.

Covariate evaluation will be performed to examine the relationship between model parameters and demographic factors (e.g., age, weight status, ethnicity) and co-administered medications, as applicable. More detail about the weight status measures used in the model will be included in the SAP. Appropriate covariates will be incorporated into the model using a standard forward inclusion-backward elimination approach. Standard model diagnostic plots and procedures will be used to evaluate model appropriateness. Model validation will be performed using visual predictive check and bootstrapping.

Using the final PK model and parameter estimates, serum concentration-time profiles of 25(OH)D will be simulated for each participant at varied dosing regimens. The percentage of participants with serum 25(OH)D greater than or equal to 40 ng/ml during a desired time period will be calculated. The best dosing regimen will be determined as the one resulted in serum 25(OH)D greater than or equal to 40 ng/ml in a majority (i.e.

75%) of participants. It is possible that the doses outlined and evaluated in this study will not end up being the dose chosen for a larger randomized, controlled, double-masked intervention trial. Creation of a PK model will determine the optimal dosing strategy in Part 2 to achieve serum vitamin D levels greater than or equal to 40 ng/ml.

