## 4 STUDY DESIGN

### 4.1 OVERALL DESIGN

The trial will comprise a Dose Finding part (Part 1) and a Dose Confirming part (Part 2). A total of 50 children age 6 years to less than 18 years were randomized to 4 cohorts (1:1:1:1) (Table 2) during Part 1. An interim PK analysis was performed when at least 4 participants in each cohort had completed PK sampling at Week 20 (visit 7; days 137-143). Interim PK analysis yielded PK parameters, and a recommended dosing regimen to achieve 25(OH)D greater than or equal to 40 ng/ml in greater than or equal to 75% of participants was determined. In Part 2, up to 63 children will be randomized to

the recommended dose (Single 50,000 IU loading dose + 8,000 IU daily dose) or a standard of care dose of 600 IU/day (2:1).

The age range of 6 to less than 18 years encompasses the major population of children who have both clinical asthma and obesity.

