## **8.2 SAFETY AND OTHER ASSESSMENTS**

Vitamin D is a very safe supplement with a large therapeutic index. Vitamin D sufficiency is considered to be greater than 30 ng/ml. Intoxication does not occur until serum 25(OH)D levels exceed 150 ng/ml (325 nmol/L).(85) However, most clinical laboratories consider 100 ng/ml to be the upper limit in order to maintain a wide safety margin. Reports of vitamin D toxicity are rare and virtually always related to faulty manufacturing or labeling of product such that individuals ingested hundreds to thousands of times the presumed dose.(86, 87) The consequence of vitamin D toxicity is hypercalcemia. Hypercalcemia only results when 25(OH)D concentrations have consistently been above 150-200 ng/ml (375-500 nmol/L).(85)

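### The dose rule in Section 9.4.2 carries no parameter uncertainty into its 75% attainment figure and, as written, can be met by several regimens

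*Combined protocol and SAP*

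**What the plan says.** Section 9.4.2 fits a population PK model and then turns it into a dose statement. The basis is given as "Using the final PK model and parameter estimates". From this, "serum concentration-time profiles of 25(OH)D will be simulated for each participant at varied dosing regimens". The percentage at or above 40 ng/ml "during a desired time period will be calculated". Then: "The best dosing regimen will be determined as the one resulted in serum 25(OH)D greater than or equal to 40 ng/ml" in a majority, specified as 75%, of participants.

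Bootstrapping is planned, but only as a check on the model: "Model validation will be performed using visual predictive check and bootstrapping". Shrinkage guides model development ("as well as objective function and shrinkage values"). Neither is linked to the dose statement.

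Elsewhere the target is a minimum. Section 4.1 reports that a regimen achieving "25(OH)D greater than or equal to 40 ng/ml in greater than or equal to 75% of participants was determined", and Section 4.3 speaks of more than 75%. On high levels, Section 8.2 notes that "most clinical laboratories consider 100 ng/ml to be the upper limit in order to maintain a wide safety margin", and Sections 7.1 and 8.2 stop study drug for an individual above 100 ng/ml. That level does not appear in 9.4.2.

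**The concern.** Three features of the rule limit what its output can support.

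- **No uncertainty.** The percentage comes from a fitted model, yet no interval is attached to it. A regimen reported at 75% may reach less in new children, and the report would not show by how much.
- **No unique answer.** Attainment of a lower threshold rises with dose. If one regimen passes 75%, higher ones pass too. A floor without a ceiling, tie-break or companion figure does not single out a best regimen.
- **No defined time.** The window is left open, whereas the Part 2 endpoint is fixed at Week 16.

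Section 2.1 says the study is to inform a later intervention trial, and Section 1 pools both parts for the PK calculations. A simulated attainment figure may therefore be carried into that design. The Part 1 choice also drew on safety and tolerability data (Section 4.3), but 9.4.2 does not repeat that input.

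**Working it through.** **The plan's own figure.** The dose rule has no stated operating characteristic to reproduce. The nearest figure is the Part 2 sample size in Section 9.2 (50% against 75%, one-group chi-square, one-sided 0.05, power 0.90):

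n = [(1.645 × √(0.5 × 0.5) + 1.282 × √(0.75 × 0.25)) / 0.25]² = 30.35, rounded up to 31. This agrees with the plan.

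With 31 completers, 20 responders give z = (0.645 − 0.5)/√(0.25/31) = 1.62, and 21 give (0.677 − 0.5)/√(0.25/31) = 1.98. The critical value is 1.645, so the test succeeds from 21/31 = 68%. Success shows attainment above 50%; it does not establish 75%.

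**Can more than one regimen qualify?** Section 4.3 cites Week 21 increments in obese adults of 27.8 (SD 10.2) ng/ml at 5,000 IU/day and 48.1 (SD 19.6) at 10,000 IU/day, and a median baseline of about 20. Assume normality and a fixed baseline of 20:

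| Regimen | Mean level | At or above 40 | Above 100 |
|---|---|---|---|
| 5,000 IU/day | 47.8 | Φ((47.8 − 40)/10.2) = 77.8% | 1 − Φ((100 − 47.8)/10.2) ≈ 0% |
| 10,000 IU/day | 68.1 | Φ((68.1 − 40)/19.6) = 92.4% | 1 − Φ((100 − 68.1)/19.6) = 5.2% |

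If the baseline SD is assumed to be 5, attainment is 75.4% and 91.8%, and the share above 100 ng/ml is about 0% and 5.7%. Both regimens pass either way. These adult figures only illustrate how the rule behaves; they are not a forecast for these children and endorse no regimen.

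**How uncertain is an apparent 75%?** The pooled maximum is 50 + 63 = 113 children (Section 4.1).

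- Treated as a count, 85/113 has a 95% Wilson interval of 67-82% (exact: 66-83%).
- Simulated attainment is not a count of observed outcomes, so a model-based check is closer. Take lognormal levels with the 50% coefficient of variation from Section 9.2, so the log-scale SD is √ln(1.25) = 0.472. Estimate mean and SD from 113 independent children. The 95% range around 75% is 68-81%.
- A regimen with true attainment of 70% would show at least 75% with probability 0.13 (binomial) or 0.08 (model-based).

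**Could attainment be overstated?** Only if individual estimates are used. Suppose their spread is (1 − s) times the true spread. An apparent 75% then corresponds to a true Φ(0.6745 × (1 − s)):

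- s = 10%: Φ(0.607) = 72.8%
- s = 20%: Φ(0.540) = 70.5%
- s = 30%: Φ(0.472) = 68.2%

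The direction follows from the target being above 50%. The values of s are assumed; the documents give none.

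**The case against.** Several points on the other side stand.

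- **Point estimates are inferred.** The model includes between-participant variability and residual error. Simulating each participant could mean using individual estimates, or it could mean random draws at each child's covariates. On the second reading the shrinkage argument falls away. A reader might infer that 9.4.2 necessarily overstates attainment; the text does not support that.
- **The data are not clearly sparse.** Section 8.1.2 requires central 25(OH)D at Visits 2 to 9, which is eight samples per child plus an optional one. Shrinkage may be small.
- **The completed Part 1 choice is not shown to be unsound.** A reader might extend the uncertainty argument to it. The documents give a minimum of 16 children for that analysis, but neither the number analysed nor the attainment found. The choice also used safety and tolerability data and data safety monitoring board approval, and the regimen is being tested in new children in Part 2.
- **9.4.2 may be partly a leftover.** Its last sentence ties the model to the dosing strategy for Part 2, and 9.4.3 repeats the paragraph almost entirely in the past tense. However, 9.4.2 is written prospectively under the study endpoint, and Section 4.3 refers to end-of-study PK modelling. The ambiguity needs settling; it does not remove the rule.
- **Nothing is adopted automatically.** 9.4.2 warns that the later trial may use another dose. A reader might infer that the rule will lead to an excessive dose; the documents do not show that. Full profiles are simulated, so the share above 100 ng/ml can be obtained. What is missing is a commitment to report it.
- **A separate SAP is announced in 9.4.1** and is not among the documents. It may add simulation detail. Even so, 9.4.2 states the decision rule in full and, on this topic, defers only the weight-status measures.

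Part 2 is a real safeguard for the 8,000 IU/day regimen with its loading dose. It offers none for a different regimen proposed from the final simulation.

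**Conclusion.** The concern holds in a limited form. As written, the rule in 9.4.2 attaches no uncertainty to the attainment percentage, leaves the time window undefined, and does not single out one regimen.

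At up to 113 children the uncertainty is moderate, about 6 to 8 points either side of 75%. The lack of a unique answer does not depend on sample size or shrinkage: on the cited adult figures two regimens pass while differing by about 5 points in the share above 100 ng/ml. Overstatement through shrinkage is possible but conditional. It would bring a true 73-68% under an apparent 75% at an assumed 10-30% shrinkage, and the documents do not allow it to be fixed more closely.

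This is a worthwhile, inexpensive improvement to the final analysis. It is not evidence that any regimen in the trial is wrong.

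**What to change.** In Section 9.4.2:

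1. Simulate new children drawn from the observed covariate distribution, with between-child and residual variability, and repeat this over the bootstrap parameter sets already planned for validation.
2. For each regimen, report the percentage at or above 40 ng/ml at Week 16 with a 95% interval and, beside it, the percentage above 100 ng/ml.
3. Do not label a regimen best on the 40 ng/ml percentage alone. The clinical choice stays with the sponsor.
4. Reconcile the closing sentence with 9.4.3: state whether it describes the completed interim step or the end-of-study analysis.

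The cost is a few more model runs and a reported attainment that may look slightly less favourable. No new data, visits or participants are needed.

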#### 9.4.3 ANALYSIS OF THE PART 1 ENDPOINT

This analysis was done including participants randomized in part 1. Dose finding was done using the PK model and parameter estimates, serum concentration-time profiles of 25(OH)D was simulated for each participant at varied dosing regimens. The percentage of participants with serum 25(OH)D greater than or equal to 40 ng/ml during a desired time period was calculated. The best dosing regimen was determined as the one resulted in serum 25(OH)D greater than or equal to 40 ng/ml in a majority (i.e. 75%) of participants. It is possible that the doses outlined and evaluated in this study will not end up being the dose chosen for a larger randomized, controlled, double-masked intervention trial. Creation of a PK model determined the optimal dosing strategy in Part 2 to achieve serum vitamin D levels greater than or equal to 40 ng/ml. The participants who achieved a vitamin D level of greater than or equal to 40 ng/ml were estimated along with the corresponding 95% confidence interval for each dose regimen in Part 1. A one-group test of proportion will be used to analyze the overall proportion of participants with 25(OH)D greater than or equal to 40 ng/ml at 16 weeks among participants treated with the final recommended dose in Part 2.

#### 9.4.4 ANALYSIS OF PART 2 ENDPOINTS

The participants who achieve a vitamin D level of greater than or equal to 40 ng/ml will be estimated along with the corresponding 95% confidence interval for each dose regimen in Part 1. A one-group test of proportion will be used to analyze the overall proportion of participants with 25(OH)D greater than or equal to 40 ng/ml at 16 weeks among participants treated with the final recommended dose in Part 2.

#### 9.4.5 SAFETY ANALYSES

All AEs recorded during the study period will be coded with Medical Dictionary for Regulatory Activities (MedDRA) Version March 2018. All participants enrolled in the study will be evaluated for safety. Summaries of AE will be tabulated for the following types:

- Number (%) of participants with any AE or AR
- Number (%) of participants with any SAE or SAR
- Number (%) of participants withdrawn from treatment due to AE

All summaries will be reported overall and by study site. Additional analyses and summaries may be derived if deemed appropriate and will be further described in the SAP.

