## 3 OBJECTIVES AND ENDPOINTS

OBJECTIVES	ENDPOINTS	JUSTIFICATION FOR ENDPOINTS
Study		
The overall objective of the study is to determine the pharmacokinetics of vitamin D supplementation in children who have asthma and are overweight or obese.	Pharmacokinetic analysis of vitamin D supplementation in children who have asthma and are overweight or obese	PK characteristics of 25(OH)D following vitamin D3 supplementation are not known in this population.
Part 1		
Identify dosing to use in Part 2 using PK analysis on a subset of participants	Serum 25(OH)D will be evaluated at Baseline and various times including post-dose elimination to determine preliminary PK analysis for the best dose for increasing vitamin D levels above 40 ng/ml in children with asthma who are overweight or obese	PK characteristics of 25(OH)D following vitamin D3 supplementation are not known in this population.
Part 2		
Determine the effectiveness of a recommended 16-week dosing regimen to achieve a serum level of 25(OH)D greater than or equal to 40 ng/ml in vitamin D insufficient or deficient children who have asthma and are overweight or obese.	Did participants in the Part 2 active dosing cohort achieve a serum 25(OH)D of greater than or equal to 40 ng/ml at 16 weeks	Serum 25(OH)D level greater than or equal to 40 ng/ml has been implicated to be anti-inflammatory.

OBJECTIVES	ENDPOINTS	JUSTIFICATION FOR ENDPOINTS
Safety		
Assess the safety and tolerability of oral vitamin D3	Adverse events (AEs), serious adverse events (SAEs), adverse reactions (ARs), and serious adverse reactions (SARs)	Assessing safety is important to determining tolerability of vitamin D in this study population.
Exploratory		

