## 7 STUDY INTERVENTION DISCONTINUATION AND PARTICIPANT DISCONTINUATION/WITHDRAWAL

### 7.1 DISCONTINUATION OF STUDY INTERVENTION

Discontinuation from taking vitamin D supplements does not mean discontinuation from the study, and remaining study procedures should be completed as indicated by the study protocol. If a clinically significant finding is identified such as an elevated urine calcium/creatinine ratio (greater than 0.37 on 2 measurements), elevated serum calcium level (greater than  $1.5 \times \text{ULN}$ ), or 25(OH)D level greater than 100 ng/ml after enrollment, the investigator or qualified designee will determine if any change in participant management is needed including discontinuation of vitamin D supplements. If a participant is discontinued from study drug (vitamin D supplement), he or she will be asked to complete any remaining study visits in order to assure his or her safety and for the sake of completeness of data collection. If a participant who has been asked to stop taking study drug terminates (for any reason) from the study, site coordinators will make reasonable efforts to complete a termination visit. The termination visit will include routine labs (safety labs at minimum) and a focused physical exam.

Rules for halting of study drug:

1. Spot urine calcium/creatinine ratio greater than 0.37 and subsequent serum calcium above  $1.5 \times \text{ULN}$  for the local laboratory. Because dehydration can artificially inflate the calcium/creatinine ratio, participants will be counseled on consuming adequate fluids throughout the study. Participants who have an elevated spot urine calcium/creatinine ratio will be asked to consume 6 to 8 eight-ounce glasses of water per day, and to return within 2 business days of the site team receiving initial lab results for a repeat calcium/creatinine ratio. If the repeat ratio is less than or equal to 0.37, study medication will be continued without interruption. If the ratio remains greater than 0.37, a local serum calcium level and local 25(OH)D will be checked. If the serum calcium is less than  $1.5 \times \text{ULN}$  and 25(OH)D is less than 100 ng/ml, the participant will continue study drug without interruption.

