If a participant develops elevated serum calcium greater than or equal to  $1.5 \times \text{ULN}$  or 25(OH)D level greater than 100 ng/ml by local lab, the participant will remain off study drug through the duration of the study, but will continue with all other study procedures. See Section 8.2 for further safety assessment information.

2. Any documented adverse event, which in the opinion of the site investigator warrants halting of study drug for participant safety.

If a participant develops elevated serum calcium greater than or equal to  $1.5 \times \text{ULN}$  or 25(OH)D level greater than 100 ng/ml, the participant will remain off study drug through the duration of the study, but will continue with all other study procedures.

The data to be collected at the time of study intervention discontinuation will include the following:

- Reason for discontinuation
- Serum 25(OH)D and serum calcium
- Urine calcium/creatinine ratio
- Concomitant medications (including vitamin D3 daily dose at screening in either individual supplement or as a part of a multivitamin)

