#### 8.3.4 TIME PERIOD AND FREQUENCY FOR EVENT ASSESSMENT AND FOLLOW-UP

The occurrence of an AE or SAE may come to the attention of study personnel during study visits and interviews of a study participant presenting for medical care, or upon review by a study monitor. All AEs including local and systemic reactions will be captured on the appropriate CRF. Information to be collected includes event description, time of onset, clinician's assessment of severity, relationship to study product (assessed only by those with the training and authority to make a diagnosis), and time of resolution/stabilization of the event. All AEs occurring while on study must be documented appropriately regardless of relationship. All AEs must be followed until 1 of the following criteria is met: resolution, the condition stabilizes, the event is otherwise explained or is judged by the PI to be no longer clinically significant, or the participant is lost to follow-up.

Any medical condition that is present at the time that the participant is screened will be considered as baseline and not reported as an AE. However, if the study participant's condition deteriorates at any time during the study, it will be recorded as an AE. Changes in the severity of an AE will be documented to allow an assessment of the duration of the event at each level of severity to be performed. AEs characterized as intermittent require documentation of onset and duration of each episode. At each study visit, the investigator or study coordinator will inquire about the occurrence of AE/SAEs since the last visit. The site investigator will record all reportable events with start dates occurring any time after informed consent is obtained. Events will be followed for outcome information until resolution or stabilization or until 7 days (for non-serious AEs) or 30 days (for SAEs) after the last day of study participation.

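### Section 9.4.5 plans AE-only safety summaries on all enrolled participants, with no first-dose window, no breakdown by regimen, and no separate count of laboratory threshold crossings or laboratory-triggered stops

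*Combined protocol and SAP*

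**What the plan says.** **Safety tables (section 9.4.5).** The named summaries are "Number (%) of participants with any AE or AR", "Number (%) of participants with any SAE or SAR" and "Number (%) of participants withdrawn from treatment due to AE". They are to be given overall and by study site; regimen is not mentioned. The same section states that "All participants enrolled in the study will be evaluated for safety". It allows further summaries in the SAP where judged appropriate.

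**Population.** Section 8.1.1.1 makes a child enrolled once consent and assent are obtained at Visit 1. Section 9.3 defines the Safety Population more narrowly, as enrolled participants with at least one dose.

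**Start of AE recording (section 8.3.4).** "The site investigator will record all reportable events with start dates occurring any time after informed consent is obtained". Section 8.3.5 continues recording until 7 days after the last day of participation.

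**Halting rules (section 7.1).** Rule 1 is the laboratory rule and begins "Spot urine calcium/creatinine ratio greater than 0.37 and subsequent serum calcium above" 1.5 × ULN; its text also covers 25(OH)D above 100 ng/ml. Rule 2 is separate: "Any documented adverse event, which in the opinion of the site investigator warrants halting of study drug for participant safety". A child stopped for serum calcium or 25(OH)D stays in the study off drug.

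**Safety endpoints (section 3).** Only AEs, SAEs, ARs and SARs are named.

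**The concern.** The protocol relies on laboratory values to detect excess vitamin D. Section 8.2 uses the urine ratio as the safety screen and describes hypercalcemia as the consequence of toxicity. The planned tables do not report these values as such. A stop under rule 1 fits the withdrawal table only if someone has also recorded an AE. Because that child stays in the study, the disposition summary in section 9.4.9, which counts completing or discontinuing the study, need not show the stop either.

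The AE tables also take in events that cannot be due to study drug: those in run-in, and those in children who consent but are never dosed. Section 8.3.3.3 lists bruising and pain from blood draws as expected AEs, and blood is drawn at screening. Without a split by regimen, children on 600 IU are pooled with those on the high-dose regimens.

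Section 2.1 says the study is to supply dosing and safety data for a later interventional trial. That trial's designers would want the frequency of threshold crossings and laboratory stops at the chosen regimen, and section 9.4.5 does not commit to giving it.

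**Working it through.** The protocol gives no figure for this point, so none can be reproduced. The check is a cross-reading, with arithmetic for size.

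**1. Which events reach a planned table**

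- *Urine ratio above 0.37.* Measured at Screening and Visits 3 to 6 (section 8.1.2). No table of its own; it counts under any AE only if a site records it.
- *Serum calcium at the 1.5 × ULN threshold.* Measured only after a repeat ratio above 0.37 (sections 7.1 and 8.2). Same position.
- *25(OH)D above 100 ng/ml.* Local levels during dosing follow a repeat high ratio or the local investigator's discretion (sections 7.1 and 8.1.2). Central levels at Visits 2 to 9 are therefore the only scheduled record during dosing. No safety table uses them, and this finding is not in the expected-AE list of section 8.3.3.3.
- *Drug halted under rule 1.* In the withdrawal table only if attributed to an AE; not necessarily in the disposition summary.

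**2. Denominator**

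Inputs from section 4.1 (maxima): enrolled 150 + 171 = 321; randomized 50 + 63 = 113. Section 6.1.2 has the first dose witnessed at the baseline visit, so randomized is close to dosed.

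For events occurring in dosed children, the percentage on all enrolled divided by the percentage on dosed is 113/321 = 0.352. With the approximate total of 107 randomized in section 1, it is 107/321 = 0.333.

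**3. Pre-dose share of the AE window**

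With run-in of d days, last visit at day 196 and 7 further days of recording, the share is d/(d + 196 + 7).

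- d = 14: 14/217 = 6.5%
- d = 7: 7/210 = 3.3%
- d = 21: 21/224 = 9.4%

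**4. Pooling over regimens (illustration)**

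Cohort A has up to 63 × 2/3 = 42 children. The documents give no event rate, so the rates below are assumptions. For simplicity, events are taken to occur in Cohort A only.

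| Assumed rate in A | Expected children | Of 63 (Part 2) | Of 113 (randomized) | Of 321 (enrolled) |
|---|---|---|---|---|
| 2% | 0.84 | 1.3% | 0.7% | 0.3% |
| 5% | 2.1 | 3.3% | 1.9% | 0.7% |
| 10% | 4.2 | 6.7% | 3.7% | 1.3% |

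On these assumptions a 10% rate at the chosen regimen would appear as 1.3% in an overall table on all enrolled. Events in other cohorts would raise the pooled figure, but it would still not show the rate at the chosen regimen.

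**The case against.** **The laboratory events are not shut out.** Section 8.3.3.3 lists raised calcium in blood or urine, and hypercalcemia, as expected AEs. Section 8.3.3.2 treats an abnormal laboratory result as a possible event, and section 7.1 calls these crossings clinically significant. A reader might infer that the tables omit dose-related laboratory events altogether; the documents do not support that. What stands is that no rule turns a threshold crossing into an AE, so in an open-label trial capture depends on the site, and a captured case disappears into the any-AE count.

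**25(OH)D is reported.** It is the core measurement of the PK analysis (section 9.4.2) and is explored further in section 9.4.10. A reader might infer that the key exposure measure goes unreported; it does not. Only the count above 100 ng/ml is missing.

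**Monitoring is narrower than it may seem.** Only the urine ratio is a scheduled safety test during dosing, at Visits 3 to 6. Serum calcium is a reflex test, and central 25(OH)D is classed as a study assessment.

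**The SAP may fill the gap.** Sections 9.4.1 and 9.4.5 defer detail to a separate SAP whose text is not in the supplied document, so the gap is shown for section 9 only. But the deferral on safety summaries is optional, and it does not remove the conflict between sections 9.3 and 9.4.5.

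**The 6.5% is a share of time, not of events.** The tables count participants, so a run-in event changes the any-AE count only if that child has no later AE. ARs are drug-caused by definition, and withdrawal from treatment cannot precede treatment. This objection is correct and limits the effect of the missing window.

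**Conclusion.** The point holds for the protocol text. Section 9.4.5 plans AE-only summaries on all enrolled participants, overall and by site, with no first-dose window and no separate summary by regimen of the monitored laboratory thresholds or of rule 1 stops. It also conflicts with the dosed Safety Population of section 9.3.

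The firmest figure is the denominator. At the stated maxima, percentages based on events in dosed children fall to about 35% of their value (33% with 107 randomized). The pre-dose share of the recording window is small, about 6.5% (3.3% to 9.4%), and should not be read as the share of AEs that precede dosing. The pooling table rests on assumed rates and shows direction only.

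This affects the clarity of the safety report. It does not bear on the Part 2 proportion test or the PK model. A SAP that already specifies these tables would settle most of it.

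**What to change.** In section 9.4.5 or the SAP:

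1. Use the section 9.3 Safety Population for all safety tables, and remove the conflicting statement about all enrolled participants.
2. Restrict the main AE tables to onset on or after the first dose. List AEs from consent to first dose separately, including those in children never dosed.
3. Report by randomized regimen, in addition to overall and by site.
4. Add, by regimen and for values on or after the first dose, the number (%) with:
   - urine ratio above 0.37, first and confirmed;
   - serum calcium crossing the protocol threshold;
   - any central or local 25(OH)D above 100 ng/ml;
   - study drug halted under each section 7.1 rule.

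Before the calcium row is programmed, the wording needs reconciling: section 7.1 uses both above, and at or above, 1.5 × ULN, and section 8.2 uses above. Which wording is intended is for the study team.

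The cost is SAP wording and a few extra tables. Section 7.1 already requires the reason for stopping, 25(OH)D, serum calcium and urine ratio to be collected when study drug is discontinued, and the other values come from existing tests. No procedure is added. Correcting the protocol's own text would need an amendment with IRB review; the extra tables can be specified in the SAP. New safety endpoints in section 3 are not needed, nor is a count above 80 ng/ml at every visit, since section 8.2 uses that level only at week 28.
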